#### 8. ARM 2 (NIVOLUMAB + IPILIMUMAB): STUDY CALENDAR & EVALUATIONS

Cycle Length: Arm 2= 42 days	Screening		On Treatment Cycle 1+ (±3)			Safety Follow up	Long Term Follow up 
	-28 d	-14 d	Day 1	Day 15 	Day 29 	30 days (±7)	(±14 days)
REQUIRED ASSESSMENTS							
Informed Consent	Х						
Medical history (inc. NGS results, if done) and Height 		Х					
Physical examination including vital signs (BP, weight)		Х	Х	Х	Х	Х	
ECOG performance status		Х	Х	Х	Х	Х	
AEs & concomitant medications 		Х	Х	Х	Х	+30, +100	Х
Radiation Treatment Plan Data 			Х				
LABORATORY TESTING							
CBC with differential and platelet count		Х	$X^4$	Х	Х	Х	
Complete Metabolic Profile		Х	X 	Х	Х	Х	
Direct bilirubin, Mg, Phos		Х	$X^4$			Х	
Creatinine clearance 		Х					
PT/INR and aPTT		Х					
Thyroid function (TSH, T3, T4) $^{6}$		Х	X 				
ESR, CRP, vWF Ag and ferritin 			preC1,C2			X 	
WOCBP: Serum or Urine pregnancy test, FSH (as needed) 		$-7d^{7}$					
DISEASE ASSESSMENT							
Pathology Report of diagnosis	X 						
CT of chest through adrenals or PET CT 	$X^{10}$		Q 12 we	eks during tre	eatment 		$X^{11}$
CT or MRI Brain 	Х						
TREATMENT EXPOSURE (Arm2)- treatment window +	/- 3 days	8					
Nivolumab 240mg Q2W			X  X 	Х	Х		
Ipilimumab 1mg/kgQ6W			X 				
CORRELATIVE STUDIES							
Mandatory Unstained Slides for Analyses, if available 	2	X					
Mandatory Whole Blood for Somatic Baseline			Pre C1				
Mandatory Blood, Serum, and Plasma for Analyses 			preC1,C2			Х	
Optional Bronchoalveolar Lavage 				Х		X 	
BANKING SAMPLES							
Optional Whole Blood 			preC1,C2			Х	
Optional Unstained Slides 		Х					
Optional Serum and Plasma 			preC1,C2			Х	
FOLLOW-UP							
Progression and survival 							Х

#### **Arm 2- Key to Footnotes**

- 1. Medical history to include include demographics, trial awareness question, smoking history, prior treatments, radiation and surgical history. Smoking history to include: amount, frequency, start and stop dates of cigarette, cigar and pipe usage. If subject has prior genetic sequencing analyses results available, those results should be submitted by end of Cycle 1.
- 2. Treatment-related adverse events will be followed until resolution, return to baseline, or deemed clinically insignificant. Adverse events (from time of consent) and concomitant medications (28 days prior to start of protocol treatment) should be assessed and recorded until 100 days after last dose of study drug. SAE's and the conmeds used to treat them will be collected up to 100 days post treatment. See Section 8.5.
- 3. Collection of radiation treatment plan data can take place any time during the study. Data such as total lung volume, V20, and additional radiation parameters will be collected. See Documents/Info tab of the EDC. This data will be recorded in the database for future analysis, but it will not affect treatment while on study and is not required to be collected prior to enrollment or initiation of treatment.
- 4. C1D1 testing does not need to be repeated if performed within 7 days of starting protocol therapy.
- 5. Measured or calculated creatinine clearance (GFR can also be used in place of creatinine or CrCl). Erythrocyte Sedimentation Rate (ESR); C-Reactive Protein (CRP); von Willebrand Factor antigen (vWF Ag). Collect ESR, CRP, vWF and ferritin pre-treatment on C1D1, C2D1 and either at the End of Treatment or if the subject develops any grade 3-4 pneumonitis.
- 6. Thyroid function testing: Perform TSH, T3, T4 at baseline and on Day 1 of each cycle (i.e. every 6 weeks). T3, T4: free/ total as per local standards.
- 7. For women of childbearing potential. Must have negative pregnancy test within 7 days of registration. Women < 62 yrs old must have FSH > 40 mIU/mL to be considered post-menopausal.
- 8. A pathology report confirming the diagnosis of NSCLC must be obtained and reviewed by the treating physician prior to registration to study.
- 9. All patients require Chest CT through adrenals or PET-CT at the time of screening and at subsequent imaging time points. Abdomen or pelvic CTs or bone scans can be included at the discretion of the treating physician should it be clinically indicated, but these are not mandatory.
- 10. Screening scan including at least CT portion of the chest and abdomen must be performed within 56 days after the completion of chemoradiation. PET CT may be done in place of regular CT scans at the discretion of the site investigator. Baseline scans should be done within 28 days prior to treatment initiation. Radiographic disease assessment will be done every 12 weeks ±4 weeks during study treatment. The scan interval may be reset if scans were done early for clinical reasons. See also 8.3.
- 11. After completion of protocol therapy, subjects who discontinue for reasons other than progressive disease will have post-treatment follow-up for disease status until disease progression, initiating a non-study cancer treatment, withdrawing consent or becoming lost to follow-up. Post treatment radiographic disease assessment should be performed every 3 months until progression. After documented disease progression each subject will be followed for survival every 3 months for up to 2 years, withdrawal of consent, or the end of the study (whichever occurs first).
- 12. A head MRI or CT should be done prior to study treatment for subjects that are symptomatic or have not had prior brain imaging.
- 13. For subjects who meet all eligibility criteria and have recovered sufficiently from treatment with chemoradiation, initial consolidation therapy with nivolumab and ipilimumab will be started within 56 days after chemoradiation is complete. For subjects who meet all eligibility criteria after completion of up to two consolidation chemotherapy treatments, therapy with nivolumab and ipilimumab will be started within 56 days after chemoradiation and ipilimumab will be started of chemotherapy.
- 14. Mandatory submission of unstained slides from an archived tumor block (if available) for PD-L1, CD4, CD8 by IHC. In addition, whole exome sequencing, RNA sequencing, methylation analysis will be performed. See CLM for collection, labeling and shipping instructions.
- 15. Mandatory blood samples for correlative testing should be drawn pre-treatment on C1D1, C2D1, and either at the End of Treatment Visit or if the subject develops any grade 3-4 pneumonitis. See CLM for collection, labeling, and shipping instructions.
- 16. If subject has a bronchoscopy with BAL for clinical reasons, please collect a portion of BAL fluid for correlative analysis (optional).
- 17. Optional submission of whole blood for banking is to be collected at Pre-Treatment C1D1, C2D1, and End of Treatment Visit. See CLM for collection, processing, labeling and shipping instructions.
- 18. Optional submission of unstained slides for banking from an archived FFPE tumor block is requested. See CLM for collection, labeling, and shipping instructions.
- 19. Optional submission of serum and plasma for banking are to be collected at Pre-Treatment C1D1, C2D1, and End of Treatment Visit. See CLM for collection, labeling, processing, and shipping instructions.

## 8.1 Screening Evaluations

## 8.1.1 Within 28 days prior to registration for protocol therapy

- Informed consent
- Pathology Report Confirmation. A pathology report confirming the diagnosis of NSCLC must be obtained and reviewed by the treating physician prior to registration to the study.
- Radiology Imaging: A CT of the chest and abdomen will be done within 56 days after chemoradiation. This imaging will be done within 28 days of treatment initiation on study. A PET CT may be done instead of regular CT scans. A head MRI or CT should be done for subjects that are symptomatic or have not had prior brain imaging of study treatment.
- Mandatory submission of unstained slides from an archived tumor block for correlative analysis, if available. New biopsy is not required if archival tissue is not available. Tissue should be identified and requested before registration; submission to BTCRC AHQ will occur after subject is successfully registered. Analysis will include PD-L1 and other IHC, and genetic analyses.
- Optional submission of unstained slides from an archived tumor block for banking, with consent. Tissue should be identified and requested before registration; submission to BTCRC AHQ will occur after subject is successfully registered.
- Collection of radiation treatment plan data can take place any time during the study. Data such as total lung volume, V20, and additional radiation parameters will be collected. See Documents/Info tab of the EDC. This data will be recorded in the database for future analysis, but it will not affect treatment while on study and is not required prior to enrollment or initiation of treatment.

## 8.1.2 Within 14 days prior to registration for protocol therapy

- Medical History. Medical history to include demographics, trial awareness question, smoking history, prior treatments, radiation and surgical history. Smoking history to include: amount, frequency, start and stop dates of cigarette, cigar and pipe usage. If subject has prior genetic sequencing analyses results available, those results should be submitted by end of Cycle 1.
- Height
- Physical examination including vital signs (blood pressure, weight)
- ECOG performance status
- Complete Metabolic Profile to include Na, K, Cl, CO2, total bilirubin, total protein, albumin, alk phos, AST, ALT, serum creatinine, BUN, calcium, and glucose. Direct bilirubin, Mg and Phos will also be drawn. Please see Section 3.1.8 for additional information regarding serum creatinine, calculated creatinine clearance and GFR values.
- Complete Blood Count with differential to include absolute neutrophil count (ANC), platelets and hemoglobin
- PT/INR and aPTT
- Thyroid function (TSH, T3, T4); T3, T4: free/ total as per local standards.
- Within 7 days: Serum or urine pregnancy test for women of childbearing potential. Women < 62 yrs old must have FSH > 40 mIU/mL to be considered post-menopausal.
- Adverse events and concomitant medications.

## 8.2 On Treatment Evaluations

## 8.2.1 Treatment Arm 1 (cycle length = 28 days)

#### 8.2.1.1 Day 1 of each cycle

- Physical examination including vital signs (blood pressure, weight)
- ECOG performance status
- Complete Metabolic Profile to include Na, K, Cl, CO2, total bilirubin, total protein, albumin, alk phos, AST, ALT, creatinine, BUN, calcium, and glucose. Direct bilirubin, Mg and Phos will also be drawn. (For C1D1 do not repeat if screening CMP is within 7 days of starting protocol therapy)
- Complete Blood Count with differential to include absolute neutrophil count (ANC), platelet and hemoglobin (For C1D1 do not repeat if screening CBC is within 7 days of starting protocol therapy).
- Thyroid function (TSH, T3, T4) (For C1D1 do not repeat if screening testing is within 7 days of starting protocol therapy). T3, T4: free/ total as per local standards.
- ESR, CRP, vWF Ag and ferritin: pre-treatment C1D1 and C2D1
- Adverse events and concomitant medications.
- Nivolumab 480 mg IV
- Blood samples for correlative testing will be drawn at pre-treatment C1D1 and C2D1.

## 8.2.1.2 Odd numbered cycles starting at Cycle 3

• Thyroid function (TSH, T3, T4) (For C1D1 do not repeat if screening testing is within 7 days of starting protocol therapy). T3, T4: free/ total as per local standards.

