#### 7. ARM 1 (NIVOLUMAB): STUDY CALENDAR & EVALUATIONS

Cycle Length: Arm 1= 28 days	Screening		On Treatment Cycle 1+	Safety Follow up	Long Term Follow up 
	-28 d	-14 d	Day 1 (±3)	30 days (±7)	(±14 days)
REQUIRED ASSESSMENTS					
Informed Consent	Х				
Medical history (inc. NGS results, if done) and Height 		Х			
Physical examination including vital signs (BP, weight)		Х	Х	Х	
ECOG performance status		Х	Х	Х	
AEs & concomitant medications 		Х	Х	+30, +100	Х
Radiation Treatment Plan Data 			Х		
LABORATORY TESTING					
CBC with differential and platelet count		Х	$X^4$	Х	
Complete Metabolic Profile	Ì	Х	$X^4$	Х	
Direct bilirubin, Mg, Phos	Ì	Х	$X^4$	Х	
Creatinine clearance 		Х			
PT/INR and aPTT		Х			
Thyroid function (TSH, T3, T4) 		Х	C1  , Every odd cycle 		
ESR, CRP, vWF Ag and ferritin 			Pre C1, Pre C2	X 	
WOCBP: Serum or Urine pregnancy test, FSH (as needed) 		$-7d^{7}$			
DISEASE ASSESSMENT					
Pathology Report of diagnosis	X 				
CT of chest through adrenals or PET CT 	X 		Q 12 weeks during Tx 		X 
CT or MRI Brain 	Х				
TREATMENT EXPOSURE (Arm1)- treatment window +/- 3	days				
Nivolumab 480mg Q4W			$X^{13}$		
CORRELATIVE STUDIES					
Mandatory Unstained Slides for Analyses, if available 	Z	K			
Mandatory Whole Blood for Somatic Baseline			Pre C1		
Mandatory Blood, Serum, and Plasma for Analyses 			Pre C1, Pre C2	Х	
Optional Bronchoalveolar Lavage 			X 		•
BANKING SAMPLES					
Optional Whole Blood 			Pre C1, Pre C2	Х	
Optional Unstained Slides 		Х			
Optional Serum and Plasma 			Pre C1, Pre C2	Х	
FOLLOW-UP					
Progression and survival 					Х

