#### **Arm 1- Key to Footnotes**

- 1. Medical history to include demographics, trial awareness question, smoking history, prior treatments, radiation and surgical history. Smoking history to include: amount, frequency, start and stop dates of cigarette, cigar and pipe usage. If subject has prior genetic sequencing analyses results available, those results should be submitted by end of Cycle 1.
- 2. Treatment-related adverse events will be followed until resolution, return to baseline, or deemed clinically insignificant. Adverse events (from time of consent) and concomitant medications (28 days prior to start of protocol treatment) should be assessed and recorded until 100 days after last dose of study drug. SAE's and the conmeds used to treat them will be collected up to 100 days post treatment.
- 3. Collection of radiation treatment plan data can take place any time during the study. Data such as total lung volume, V20, and additional radiation parameters will be collected. See Documents/Info tab of the EDC. This data will be recorded in the database for future analysis, but it will not affect treatment while on study and is not required to be collected prior to enrollment or initiation of treatment.
- 4. C1D1 testing does not need to be repeated if performed within 7 days of starting protocol therapy.
- 5. Measured or calculated creatinine clearance (GFR can also be used in place of creatinine or CrCl). Erythrocyte Sedimentation Rate (ESR); C-Reactive Protein (CRP); von Willebrand Factor antigen (vWF Ag). Collect ESR, CRP, vWF and ferritin pre-treatment on C1D1, C2D1 and either at the End of Treatment or if the subject develops any grade 3-4 pneumonitis.
- 6. Thyroid function testing: Perform TSH, T3, T4 at baseline and at odd cycles starting at cycle 3 (i.e. Q 8 wks). T3, T4: free/ total as per local standards.
- 7. For women of childbearing potential. Must have negative pregnancy test within 7 days of registration. Women < 62 yrs old must have FSH > 40 mIU/mL to be considered post-menopausal.
- 8. A pathology report confirming the diagnosis of NSCLC must be obtained and reviewed by the treating physician prior to registration to study.
- 9. All patients require Chest CT through adrenals or PET-CT at the time of screening and at subsequent imaging time points. Abdomen or pelvic CTs or bone scans can be included at the discretion of the treating physician should it be clinically indicated, but these are not mandatory.

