## 8.4 Safety Follow-up Evaluations

A safety follow-up visit should occur when subjects permanently stop study treatment for whatever reason (toxicity, progression, or at discretion of site investigator) and should be performed 30 days ( $\pm$ 7 days) after the last dose of treatment. Subjects who have an ongoing  $\geq$  grade 2 or serious AE (SAE) at this visit will continue to be followed until the AE resolves to  $\leq$  Grade 1 or baseline, is deemed clinically insignificant, and/or until a new anti-cancer treatment starts, whichever is earlier.

- Physical examination including vital signs (blood pressure, weight)
- ECOG performance status
- Complete Metabolic Profile
- Complete Blood Count with differential
- ESR, CRP, vWF Ag and ferritin
- Adverse events, and concomitant medications must be assessed. Treatment-related adverse events will be followed until resolution, return to baseline, or deemed clinically insignificant. Adverse events (from time of consent) and concomitant medications (28 days prior to start of protocol treatment) should be assessed and recorded until 100 days after last dose of study drug. SAE's and the conmeds used to treat them will be collected up to 100 days post treatment. See Section 8.5 below.
- Mandatory blood samples for correlative testing and optional samples for banking will be drawn

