## **Endocrinopathies**

Endocrinopathies have been observed following treatment with nivolumab. Most cases were of low or moderate grade. The events have typically been identified through either routine periodic monitoring of specific laboratories (e.g., TSH) or as part of a work-up for associated symptoms (e.g., fatigue). Events may occur within weeks of beginning treatment, but also have been noted to occur after many months (while still on treatment). More than 1 endocrine organ may be involved (e.g., hypophysitis [pituitary inflammation] may need to be evaluated at the time adrenal insufficiency or thyroid disorder is suspected). Moderate- to high-grade cases were managed with hormone replacement therapy and, in some cases, with the addition of corticosteroids. In some cases, nivolumab treatment was held until adequate hormone replacement was provided.

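### The 30-day safety visit has no thyroid test, so subjects who stop before C3D1 (Arm 1, odd-cycle schedule) or C2D1 (Arm 2) have none scheduled after dosing

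*Combined protocol and SAP*

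**What the plan says.** **Arm 1 on treatment.** The Section 7 calendar puts thyroid function at C1 and "Every odd cycle". Footnote 6 reads "Perform TSH, T3, T4 at baseline and at odd cycles starting at cycle 3 (i.e. Q 8 wks". Section 8.2.1.2, headed "Odd numbered cycles starting at Cycle 3", agrees. Section 8.2.1.1, which covers Day 1 of every cycle, also lists "Thyroid function (TSH, T3, T4) (For C1D1 do not repeat if screening testing is within 7 days of starting protocol therapy", with no limit to particular cycles. Section 8.2.1.2 repeats that bullet, including a C1D1 waiver that cannot apply from cycle 3 onward.

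**Arm 2 on treatment.** The Section 8 calendar, its footnote 6 and Section 8.2.2.1 all schedule thyroid function on Day 1 of each 6-week cycle. Section 8.2.2.2 lists none on Days 15 and 29.

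**After treatment.** Section 8.4 states: "A safety follow-up visit should occur when subjects permanently stop study treatment for whatever reason". The visit falls 30 days (±7) after the last dose. Its laboratory list has a metabolic profile, blood count, ESR, CRP, vWF antigen and ferritin, and "Mandatory blood samples for correlative testing and optional samples for banking will be drawn". TSH, T3 and T4 are not listed. The thyroid row is blank at safety follow-up in both calendars, and Section 8.5 schedules no thyroid test.

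**Why thyroid tests are done.** Section 11.1.8 (Endocrinopathies) says: "The events have typically been identified through either routine periodic monitoring of specific laboratories (e.g., TSH", or else through a work-up for symptoms. On timing it says: "Events may occur within weeks of beginning treatment, but also have been noted to occur after many months (while still on treatment".

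**The concern.** Toxicity is a secondary objective, and the Safety population in Section 13.4 includes everyone who takes at least one dose. A subject who stops early is counted there, yet may never have a planned thyroid test after exposure. For that subject, one of the two usual detection routes named in Section 11.1.8 is absent by design. Early stopping is foreseeable: the Section 6.1 table requires permanent discontinuation for grade 3 or 4 pneumonitis, for example.

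At stake is recognition of a treatable condition in individual patients and, secondarily, completeness of the toxicity tables. Under Section 12.1.1, an abnormal laboratory value that needs treatment or further tests is an adverse event, so thyroid dysfunction needing hormone replacement would be recorded if it were found.

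The conflict between Section 8.2.1.1 and the other Arm 1 entries is a separate and smaller matter. It leaves sites with two schedules, but resolving it would not close the gap at the end of treatment.

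**Working it through.** This is schedule arithmetic on nominal days, assuming no dose delays.

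**Inputs**
- Arm 1: 28-day cycles, up to 6 (Section 5.2.3.1).
- Arm 2: 42-day cycles, up to 4; nivolumab on Days 1, 15 and 29, ipilimumab on Day 1 (Sections 5.2.4.1 and 5.2.4.2).
- Safety visit: last dose + 30 days, ±7 (Section 8.4).
- On-treatment imaging: every 12 weeks, ±4 weeks (Section 8.3).
- Planned enrollment: 54 in Arm 1 and 51 in Arm 2 (Section 13.3).

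**The plan's own figure.** Odd cycles are 2 × 28 = 56 days apart, which is 8 weeks. This matches footnote 6.

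**Arm 1.** Dose k falls on day 28(k − 1): days 0, 28, 56, 84, 112 and 140. On the odd-cycle schedule, the tests after the first dose are C3D1 (day 56) and C5D1 (day 112). Read literally, Section 8.2.1.1 gives k − 1 tests after the first dose. Scheduled tests after the first dose, by number of doses received:

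| | 1 | 2 | 3 | 4 | 5 | 6 |
|---|---|---|---|---|---|---|
| Odd-cycle, next Day 1 not reached | 0 | 0 | 1 | 1 | 2 | 2 |
| Odd-cycle, next Day 1 reached but not dosed | 0 | 1 | 1 | 2 | 2 | n/a |
| Section 8.2.1.1 read literally, next Day 1 not reached | 0 | 1 | 2 | 3 | 4 | 5 |
| Odd-cycle plus safety visit, next Day 1 not reached | 1 | 1 | 2 | 2 | 3 | 3 |

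Three things follow.
- The zeros sit at 1 and 2 doses. A 2-dose subject who attends C3D1, is tested and is then not dosed has 1 test.
- A 1-dose subject who does not reach C2D1 has 0 tests on either reading, so settling the wording alone does not help that subject.
- A full-course subject has 2 or 5 tests, depending on which section the site follows.

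**Arm 2.** Day 1 of cycle c falls on day 42(c − 1): days 0, 42, 84 and 126. A subject who stops in cycle c before the next Day 1 has c − 1 tests after the first dose: 0, 1, 2 or 3 for cycles 1 to 4. Adding the safety visit gives 1, 2, 3 or 4. A subject who stops before C2D1 can have had 1 ipilimumab dose (day 0) and up to 3 nivolumab doses (days 0, 14 and 28) with no scheduled test after dosing.

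**When an added test would fall.**
- Arm 1, 1 dose: day 0 + 30 = 30 (23 to 37).
- Arm 1, 2 doses: day 28 + 30 = 58 (51 to 65).
- Arm 2, stopping in cycle 1 with the last dose on day 0, 14 or 28: day 30, 44 or 58, each ±7.

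**Who is exposed.** The first planned scan falls at weeks 12 − 4 = 8 to 12 + 4 = 16. Arm 1 C3D1 is day 56 (week 8) and Arm 2 C2D1 is day 42 (week 6). Progression on a planned scan would therefore seldom stop a subject before the relevant test visit; the exception is visit-window overlap around week 8 in Arm 1. Those left are mainly subjects who stop for toxicity, withdrawal or clinically prompted early progression.

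**The case against.** The strongest reply is that nothing about the safety visit is contradictory. Section 8.4 and both calendars omit thyroid testing consistently, and no section requires it at the end of treatment. That is correct: this is a design choice that can be improved, not an error.

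It is also fair that early stoppers are not left unobserved. Examination, performance status, a metabolic profile and adverse event review take place at the safety visit, and testing for symptoms remains open. A subject stopped for toxicity will often be under work-up already. The endocrinopathy algorithm in Appendix 1 is a figure not available here, so its testing advice cannot be judged. Under Section 12.2.1, asymptomatic abnormalities that need no treatment are not collected, and collection ends when new anti-cancer therapy starts. A day-30 result would therefore add nothing to the toxicity tables for some subjects. These points limit the gain without removing it: an early stopper with few symptoms and a treatable abnormality still has no planned test.

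A reader might infer more than the documents support:
- **That the safety visit falls inside a known onset window.** Section 11.1.8 speaks only of weeks and gives no numerical range. The days above show when a test would occur, not how many events it would detect.
- **That ipilimumab thyroid events are known to appear after stopping.** The late-onset remark in Section 11.2.8 covers all inflammatory events of the drug, across several organs. It is not specific to the thyroid.
- **That the Section 8.2.1.1 bullet causes under-testing.** It is probably a leftover line, and a site that follows it tests more often than the calendar asks.

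**Conclusion.** The concern holds as a cheap improvement to safety monitoring. Scheduled thyroid tests after dosing number 0 for an Arm 1 subject who stops after 1 or 2 doses without reaching C3D1 on the odd-cycle schedule, and 0 for an Arm 2 subject who stops before C2D1. With the test added to the safety visit, each has 1.

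The counts assume nominal visit days, the odd-cycle schedule as the intended one for Arm 1, and attendance at the safety visit. They describe scheduled tests only. The documents give neither an early-stopping rate nor a thyroid-event rate, so they do not support any claim that a particular number of diagnoses would be missed or that reported toxicity rates would be materially wrong. The primary PFS analysis, the sample size and the stopping rules in Section 13.8 are unaffected. The Arm 1 wording conflict is editorial.

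**What to change.** **Main change.** Add TSH, T3 and T4 to the 30-day safety visit in Section 8.4, to the safety follow-up cell of the thyroid row in both calendars, and to footnote 6 of both arms.

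**Tidy-up in the same amendment.** Limit the thyroid bullet in Section 8.2.1.1 to C1D1, and delete the C1D1 waiver from Section 8.2.1.2. This should not go in alone: without the safety-visit test, it would settle at 0 the 2-dose count that a literal reading of Section 8.2.1.1 puts at 1.

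**Cost.** At most one extra panel per subject, 54 + 51 = 105 in all, at a visit where blood is already drawn. The text edits need a routine protocol amendment, with IRB notification by each site under Section 16.1.
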